### **2. Size of sample**

Total number of subjects planned to be included in this study: 214

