### **5. Study design**

#### **5.1 Study design**

The *MIEL* study is a multi-centre, prospective, randomized, open-label, blinded endpoint (PROBE) trial with a non-inferiority design. The study process was permitted by the ethics committee.

The study's emergency green channel team screened patients at 6-24 hours of onset for possible large vessel occlusion based on head CT scan and NIHSS score of  $\geq 6$  as the proposed cohort. Patients who met the entry criteria were then randomized 1:1 by the arriving stroke specialist into two groups 1 and 2 as follows, with the order of randomization being the responsibility of an independent investigator.

1.The MRI group performed DWI, FLAIRE, T1, T2 and MRA sequences.

2.The Control group underwent MRA or CTA, perfusion sequences, and F-stroke software (Brain Seal Smart Technology).

All patients were treated with standard Endovascular therapy and or optimal

drug therapy. The primary outcome was the overall distribution of modified Rankin scale scores at 90 days after surgery in the two groups of patients with modified intention-to-treat (**mITT**, defined as patients who had been optimally treated for acute macrovascular occlusion), as assessed by adjusted common odds ratios. Multiple secondary outcomes, including death, symptomatic intracranial hemorrhage, and ischemic regional reperfusion, were also assessed in the included study population.

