### 5.33 Study Implementation Process

Patient enrollment methods:

- A) Emergency greenway triage based on signs and symptoms and NCCT: In this study, a team of emergency department neurologists screened patients for possible large vessel occlusion at 6-24 hours of onset based on head CT scan and NIHSS score  $\geq 6$  and RACE score  $\geq 5$  as proposed subjects.
- B) Clearly diagnosed acute large vessel occlusion (ELVO)

Patients who have performed one of the MRI plain or perfusion examinations but do not meet the inclusion criteria for the DAWN or DEFUSE3 studies may be considered for inclusion. After enrollment, the appropriate imaging modality was selected according to the group as the basis for whether or not to perform interventional treatment.

Screening may be included in cases where either MRI or perfusion imaging is available at the time of the stroke specialist's evaluation of the patient, but the patient or authorized delegated family member is temporarily unable to decide whether to undergo the procedure, or under special irresistible conditions such as occupancy of the interventional suite.

Patients who met the entry criteria were then randomized 1:1 by the arriving stroke specialist into two groups 1 and 2 as follows, with the order of randomization being the responsibility of an independent investigator.

1. The MRI group performed DWI, FLAIRE, T1, T2 and MRA sequences.
2. The Control group underwent MRA or CTA, perfusion sequences, and F-stroke software (Brain Seal Smart Technology).

After randomization, the attending interventionalist decided the treatment based on the history and imaging data of the respective group. All patients were treated with the standard embolization procedure and or the optimal drug therapy. The primary outcome was the overall distribution of **MITT** patients' modified Rankin Scale scores at 90 days postoperatively in both groups, as assessed by the corrected co-ratio. Multiple secondary outcomes, including death, symptomatic intracranial hemorrhage, and

ischemic regional reperfusion, and safety outcomes were also assessed for the included study population.

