#### **5.34 Statistical methods**

The primary efficacy analyses were performed by shift analysis, applying cumulative ordinal logistic regression to estimate the common OR and to evaluate the improvement in mRS scores in the **mITT** population. For secondary efficacy and safety analyses, statistical significance of differences between groups was assessed by Pearson  $\chi^2$  test or Fisher exact test for categorical variables, and by t test or Mann-Whitney test for continuous variables and safety endpoints for all patients. Descriptive analyses of adverse events were presented in the form of totals and events. Multivariate logistic or ordinal regression analyses were applied to determine independent estimators of good functional outcomes and were expressed as OR values and their 95% confidence intervals (95% CI). Two-sided values of  $P < 0.05$  were considered statistically significant. All statistical analyses were performed with IBM SPSS Statistics for Windows, version 19 (IBM Corp).

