### **5.37 Outcomes**

The primary outcome was the modified Rankin Scale score (mRS 90d) of a randomized group of modified intention-to-treat (mITT) patients (defined as patients with acute macrovascular occlusions treated optimally with endovascular or pharmacologic therapy) at 90 days (with an assessment time window of  $\pm 14$  days) and analyzed for noninferiority. If the primary analysis indicated possible superiority, superiority was tested as a secondary objective. Data were collected by structured interviews (telephone interviews) with patients using a standardized form by trained physicians who were unaware of the subgroup results. A standardized written report of each interview was presented to two members of the outcome committee, who confirmed the scores and reached agreement.

The secondary outcomes were as follows:

Proportion of patients in each group receiving interventions Good prognosis for patients receiving interventions

- 1) Patient death within 90 days.
- 2) Successful reperfusion after embolization, defined as an extended Thrombolysis in Cerebral Infarction (eTICI) score of 2b, 2c or 3 at the time of the first intracranial angiogram.
- 3) Percentage of patients revascularized 24 to 72 hours after surgery (as determined by CTA).
- 4) NIHSS scores at 24 hours and 5 to 7 days postoperatively (or at discharge).
- 5) Final infarct volume (calculated by CBV or DWI) at 24 hours and 5 to 7 days postoperatively (or at discharge).
- 6) Comparison of modified Rankin scores at 90 days (0 or 1 vs. 2-6; 0-2 vs. 3-6; 0-3 vs. 4-6; 0-4 vs. 5 or 6; and 0-5 vs 6).
- 7) Quality of life assessment at 90 days: European Five Dimensions and Five Levels Scale (EQ-5D-5L) scores (range, -0.39 [worst] to 1.00 [best]); Barthel

Index scores at 90 days (range, 0 [severe disability] to 100 [no disability]).

Safety outcomes: included all hemorrhage and symptomatic intracranial hemorrhage (Judged by the Heidelberg Classification of Hemorrhage); intraoperative arterial puncture site pseudoaneurysm and inguinal hematoma, cerebral infarction in an additional vascular area at 5 to 7 days, and death within 90 days. The timing of clinical evaluation included at baseline, 24 hours after randomization, 5 to 7 days, or at discharge, whichever occurred first, and 90 days (with an assessment time window of  $\pm 14$  days).

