##### **5.42 Prior to randomization**

The following data must be collected for all subjects prior to randomization and registration:

Confirmation that all enrolled patients meet the inclusion/exclusion criteria.

Demographic information and past history.

Vital signs.

Neurological function tests (NIHSS score, mRS score).

Routine blood count, blood biochemistry and coagulation.

Neuroimaging: MRI/CT to assess for intracranial hemorrhage; MRA/CTA/DSA to confirm that the occlusion occurred in a large vessel of the anterior circulation, such as the internal carotid artery (ICA) or the M1 segment of the middle cerebral artery.

**Determination of time points:** For consistency and clarity, a time standard was established for this study, namely time 0 "t = 0" defined as the time of randomization; that is, after CT exclusion of intracranial hemorrhage and suspicion of acute anterior great vessel occlusion (ICA or MCA-M1) based on clinical signs and symptoms, all subsequent time points (e.g., 24 hours, first day of the week, and second day of the week) were determined. All subsequent time points (e.g., 24 hours, days 5-7, 30, and 90) were used as a

reference for randomization time (t=0). Time recording format: X day, X month, X month, X hour, X minute.

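### The five 90-day mRS cuts get unadjusted tests although the primary analysis of the same scale is adjusted: valid, but with some avoidable loss of power and comparability

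*Protocol*

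**What the plan says.** **Primary analysis.** Section 5.1 has the overall 90-day mRS distribution compared "as assessed by adjusted common odds ratios". Section 5.33 repeats this in a garbled form, "as assessed by the corrected co-ratio", which most plausibly means the same measure. Section 5.34 names a cumulative ordinal logistic model for the common OR but mentions neither adjustment nor covariates.

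**The five cuts.** Section 5.37, item 6, lists as a secondary outcome "Comparison of modified Rankin scores at 90 days (0 or 1 vs. 2-6; 0-2 vs. 3-6; 0-3 vs. 4-6; 0-4 vs. 5 or 6; and" a fifth cut, 0-5 against 6.

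**Their test.** Section 5.34 states that for secondary efficacy and safety analyses "statistical significance of differences between groups was assessed by Pearson" chi-square or Fisher exact tests if the variable is categorical. Neither test takes covariates.

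**The other regression in 5.34.** Multivariate logistic or ordinal models, with ORs and 95% CIs, are planned to find independent predictors of good outcome. Neither the comparison of arms nor the five cuts is mentioned there.

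**Baseline data.** Section 5.42 requires, before randomization, demographics and "Neurological function tests (NIHSS score, mRS score". Age and pre-onset mRS are also entry criteria in section 5.2.1.

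**The concern.** The same scale is analysed with adjustment once and without it five times, and no reason is given. The protocol fixes this choice itself; it does not leave it to an analysis plan.

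Two things are at stake. The first is power: a strong baseline predictor explains outcome variation that an unadjusted test leaves in the noise. The second is comparability. The cuts are where a reader looks to see whether one common OR describes the scale, and 0-2 vs 3-6 is the result most likely to be quoted. ORs are non-collapsible: with prognostic covariates and a real effect, the marginal OR lies closer to 1 than the conditional OR for the same effect. A gap between a cut's crude OR and the primary OR could then come from the change of measure or from a departure from proportional odds, and the reader could not tell which.

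**Working it through.** **Inputs from the protocol.** "Total number of subjects planned to be included in this study: 214" (section 2) and 1:1 allocation (section 5.1) give 214 / 2 = 107 per arm. The test is two-sided at 0.05 (section 5.34). The protocol gives no power, effect size, margin, mRS distribution or covariate strength, so the 214 cannot be reproduced. 107 per arm is an upper bound wherever a cut is analysed in the modified intention-to-treat set.

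**Assumptions, for illustration only.** Control-arm proportion 45% for mRS 0-2 and 83% for mRS 0-5; conditional OR 1.77 or 2.2; one standard normal baseline score x with log-odds slope b = 0, 0.5, 1.0 or 1.5 per SD.

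**Model.** logit P(good outcome) = a + ln(OR) × arm + b × x, with a set so that the control proportion, averaged over x, equals the assumed value. The marginal OR is [p1 / (1 − p1)] / [p0 / (1 − p0)], where p0 and p1 are averaged over x. Example with OR 1.77 and b = 1.0: p0 = 0.450 and p1 = 0.567, so (0.567 / 0.433) / (0.450 / 0.550) = 1.310 / 0.818 = 1.60.

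**Results for mRS 0-2** (600 simulated trials per row):

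| Conditional OR | b | Marginal OR | Power, chi-square | Power, adjusted logistic | Gain (points) |
|---|---|---|---|---|---|
| 1.77 | 0 | 1.77 | 54.5% | 55.0% | 0.5 |
| 1.77 | 0.5 | 1.71 | 52.3% | 55.0% | 2.7 |
| 1.77 | 1.0 | 1.60 | 41.0% | 46.8% | 5.8 |
| 1.77 | 1.5 | 1.50 | 30.3% | 42.0% | 11.7 |
| 2.2 | 0 | 2.20 | 79.3% | 79.5% | 0.2 |
| 2.2 | 0.5 | 2.11 | 78.2% | 80.7% | 2.5 |
| 2.2 | 1.0 | 1.92 | 63.8% | 73.3% | 9.5 |
| 2.2 | 1.5 | 1.75 | 54.7% | 68.0% | 13.3 |

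The simulation standard error of one power figure is at most √(0.5 × 0.5 / 600) = 2 points. Both tests were run on the same simulated data, so their difference is more precise than two separate runs would give.

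**mRS 0-5 vs 6.** Over the same scenarios the adjusted model's advantage runs from about −2 to +5 points. It is near zero unless the covariate is strong.

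**Second parameterisation.** Here the intercept is −0.2 and the score has correlation ρ with the latent outcome, so that b = √[ρ² / (1 − ρ²) × π² / 3]; ρ = 0.3, 0.5 and 0.6 give b = 0.57, 1.05 and 1.36. At OR 2.0, chi-square against adjusted power is 63.4% vs 67.0%, 53.2% vs 61.5% and 44.8% vs 58.7%. At OR 1.0 both reject in 4.3% to 5.2% of trials, so both hold their level.

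**Similar arms** (same model, 1,500 trials each):

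| Conditional OR | ρ = 0.3, chi-square vs adjusted | ρ = 0.5, chi-square vs adjusted |
|---|---|---|
| 1.2 | 8.1% vs 8.1% | 7.9% vs 8.3% |
| 1.3 | 14.5% vs 16.6% | 11.2% vs 12.7% |
| 1.5 | 26% vs 28% | 21% vs 27% |

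Up to OR 1.3 the gain is about 0 to 2 points, which is within or near simulation error. At conditional OR 1.2 the marginal OR is 1.19 (ρ = 0.3) or 1.16 (ρ = 0.5). At OR 1 the two coincide.

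**The case against.** **The tests are valid and conventional.** This stands. Their type I error is correct, and a marginal OR is a legitimate quantity. The shrinkage is non-collapsibility, not bias, and a risk difference would not show it. The planned tests yield p-values, and 5.34 asks for no crude OR; the comparability problem arises only when someone computes one from the tables.

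**The larger gains assume effects that this trial may not see.** This is a "trial with a non-inferiority design" comparing two imaging strategies, and superiority is tested only conditionally (section 5.37). With similar arms the gain is close to nothing. This stands and limits the severity.

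**Dilution favours non-inferiority.** A reader might infer that crude ORs nearer to 1 help the MRI strategy pass. The documents do not support that. Section 5.37 attaches non-inferiority to the primary mRS analysis, which section 5.1 adjusts, and no non-inferiority conclusion rests on the cuts.

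**The cuts must disagree with the primary result.** A reader might infer this too, but it does not follow. The gap needs prognostic covariates and a non-null effect, and near OR 1.2 it is too small to notice with 214 patients.

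**5.34 already offers adjusted models.** Only in part. The sentence is worded as a predictor analysis and does not cover the five cuts, although treatment arm could be a term in such a model.

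**5.34 does not call the primary model adjusted.** True. The contrast rests on sections 5.1 and 5.33, and the protocol names no covariates for either analysis, so the fix has to name them.

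**Conclusion.** The point holds as a low-severity improvement. The protocol fixes unadjusted tests for five cuts of a scale whose primary analysis it adjusts, although suitable covariates are recorded before randomization. For mRS 0-2 at conditional ORs of 1.77 to 2.2, the power given up is about 2 to 3 points with weak covariates, 6 to 10 with moderate ones and 12 to 13 with strong ones. It is about 0 to 2 points when the arms are similar, and little for 0-5 vs 6. A crude OR would read 1.71 to 1.50 where the conditional OR is 1.77, and 2.11 to 1.75 where it is 2.2.

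All of these sizes rest on assumed outcome rates, effects and covariate strengths, and on the full 107 per arm. None can be derived from the protocol. Nothing here makes the planned tests wrong or threatens the primary conclusion.

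**What to change.** In section 5.34, state that the arms are compared on each of the five mRS cuts by binary logistic regression with the same baseline covariates as the primary ordinal model, and report the adjusted OR with its 95% CI. Name those covariates in 5.34 for both analyses, for example age, baseline NIHSS and pre-onset mRS, and say there that the primary model is adjusted, so that it agrees with sections 5.1 and 5.33. Keep the chi-square or Fisher result as a supplement.

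The cost is one or two sentences. Logistic regression is already in 5.34 and no new data are needed. The small downside is that a sparse cut, most likely 0-5 vs 6, may need fewer covariates or a penalized fit; a rule for that should be set in advance.

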#### **5.35 Evaluation criteria for embolization procedures**

MRI group: patient meets the criteria for entry; MRA meets the criteria for large vessel occlusion; and one of the following criteria is met: 1) presence of FVH-DWI mismatch sign (see Appendix) and infarct volume  $< 70$  ml; 2) inability to obtain FLAIR sequence or to determine whether there is a FVH-DWI mismatch using the following criteria: patients  $\geq 80$  years old, preoperative NIHSS  $\geq 6$  points, DWI infarct volume  $< 21$  ml, 2) patients  $< 80$  years old, preoperative NIHSS  $\geq 6$  points, DWI infarct volume  $< 31$  ml, 3) patients  $< 80$  years old, preoperative NIHSS  $\geq 6$  points, DWI infarct volume  $< 31$  ml 3) patients  $< 80$  years old with preoperative NIHSS  $\geq 20$  and DWI infarct volume less than 51 ml (see Appendix [9] for infarct volume evaluation methods); 3) patients with other conditions where MRI infarct volume cannot be determined, where MRI has failed, or where patients with atypical posterior circulation stroke are included are judged by operator experience as to whether to perform surgical treatment; Control group. Patients met the inclusion criteria; MRA/CTA was consistent with large vessel occlusion; preoperative NIHSS  $\geq 6$ ; F-Stroke (CBV  $< 70$  mL; mismatch ratio  $\geq 1.8$ ; mismatch volume  $> 15$  ml). CTA and CT perfusion were preferred in the Control group. The above results were evaluated by two neurointerventional specialists based on the readings provided by the respective groups, and the decision to perform the procedure was made by a third senior neurointerventional specialist in case of disagreement.

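### For patients randomised on suspicion of occlusion, entry to the primary mITT set can be decided after randomisation by a vessel test that differs between the arms

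*Protocol*

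**What the plan says.** **The analysis set.** Protocol 5.1 describes the mITT set as "defined as patients who had been optimally treated for acute macrovascular occlusion". Section 5.37 describes it as "defined as patients with acute macrovascular occlusions treated optimally with endovascular or pharmacologic therapy". Both wordings require an occlusion. The primary outcome in this set is to be "analyzed for noninferiority", and 5.34 runs the shift analysis by "applying cumulative ordinal logistic regression to estimate the common OR and to evaluate the improvement in mRS scores in the" mITT population. Section 5.43 otherwise mentions only a per-protocol set. No ordinal mRS comparison in all randomised patients is stated.

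**Entry.** The inclusion criteria in 5.2.1 rest on NIHSS, RACE and CT ASPECTS and do not ask for a confirmed occlusion. Section 5.33 gives two routes: A, possible occlusion judged on symptoms and non-contrast CT; B, occlusion already clearly diagnosed.

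**The vessel test.** In 5.1 and 5.33 the arm-specific imaging comes after randomisation. In 5.35 the MRI group qualifies for the procedure if "MRA meets the criteria for large vessel occlusion", and the control group if "MRA/CTA was consistent with large vessel occlusion". For the work-up, 5.1 says "The Control group underwent MRA or CTA, perfusion sequences, and F-stroke software", and 5.35 adds that "CTA and CT perfusion were preferred in the Control group".

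**The contrary line.** Section 5.42 lists confirmation of the occlusion by MRA, CTA or DSA among the data needed before randomisation. The same section defines time 0 as randomisation, following exclusion of haemorrhage on CT and clinical suspicion of an occlusion.

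**The concern.** An analysis set keeps the protection of randomisation if the rule for dropping patients uses only information fixed before allocation, or information obtained in the same way in both arms. Here the rule is whether an occlusion was found. For route A patients, the text of 5.1, 5.33 and the time-0 definition leaves that to a test chosen by allocation. MRA and CTA need not make the same errors. If they do not, the two mITT groups can differ in two ways: in how many patients without a true occlusion they keep, and in how many true occlusions they lose. Either difference can shift the common odds ratio for reasons unrelated to how well each strategy selects patients for treatment. In a non-inferiority trial even a small shift matters, because it may move the estimate towards or away from the margin.

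This is separate from the meaning of optimal treatment in the mITT definition. It would remain if that condition were defined precisely or removed.

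**Working it through.** **Step 1. Order of events.**

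- 5.1 and 5.33: screen on CT and clinical scores, randomise 1:1, then image according to group.
- 5.42, time 0: randomisation follows CT and clinical suspicion. This agrees with 5.1 and 5.33.
- 5.42, data list: vessel confirmation before randomisation. This disagrees with all of the above.
- 5.33, route B: occlusion known at entry, so status does not depend on the arm.

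The point therefore holds for route A patients, unless the 5.42 data list governs. The protocol does not say what fraction of patients will enter by route A.

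**Step 2. Illustration of size.** The protocol gives no accuracy figure for either test as used in the trial, so only the 214 patients and the 1:1 ratio (107 per arm) come from it. The rest is assumed: share truly occluded p = 0.60; MRA sensitivity (Se) 0.90 and specificity (Sp) 0.85 to 0.95; CTA sensitivity 0.97 and specificity 0.98; patients without occlusion 20 points more likely to have a good outcome. All patients are taken as route A and all controls as having CTA, which is the extreme case.

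Non-occluded share of mITT = (1 − p)(1 − Sp) / [p·Se + (1 − p)(1 − Sp)].

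- MRI arm, Sp 0.95: 0.40 × 0.05 = 0.02; 0.60 × 0.90 = 0.54; 0.02/0.56 = 3.6%.
- MRI arm, Sp 0.85: 0.40 × 0.15 = 0.06; 0.06/0.60 = 10.0%.
- Control: 0.40 × 0.02 = 0.008; 0.60 × 0.97 = 0.582; 0.008/0.590 = 1.4%.

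False-positive part of the bias: (3.6 − 1.4) × 0.20 = 0.4 points, to (10.0 − 1.4) × 0.20 = 1.7 points, in favour of MRI.

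**Step 3. Other assumed values**, same 20-point gap. Accuracy is sensitivity/specificity.

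| p | MRA vs CTA accuracy | Non-occluded share, MRI vs control | False-positive part |
|---|---|---|---|
| 0.50 | 0.90/0.90 vs 0.95/0.95 | 10.0% vs 5.0% | 1.0 |
| 0.50 | 0.85/0.85 vs 0.97/0.97 | 15.0% vs 3.0% | 2.4 |
| 0.70 | 0.90/0.90 vs 0.95/0.95 | 4.5% vs 2.2% | 0.5 |
| 0.70 | 0.85/0.85 vs 0.97/0.97 | 7.0% vs 1.3% | 1.1 |
| 0.90 | 0.90/0.90 vs 0.95/0.95 | 1.2% vs 0.6% | 0.1 |
| 0.90 | 0.85/0.85 vs 0.97/0.97 | 1.9% vs 0.3% | 0.3 |

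With equal accuracy in both arms the difference is zero.

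**Step 4. Missed occlusions.** On the Step 2 inputs each arm has 107 × 0.60 = 64.2 true occlusions. MRA misses 10% (6.4 patients) and CTA 3% (1.9). Suppose, again as an assumption, that missed occlusions do 20 points better than detected ones. Relative to the mean of all true occlusions, detected ones then average 0.10 × 20 = 2.0 points lower in the MRI arm and 0.03 × 20 = 0.6 lower in control. Take non-occluded patients as 20 points above the same mean.

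- MRI arm, Sp 0.95: 0.964 × (−2.0) + 0.036 × 20 = −1.2.
- MRI arm, Sp 0.85: 0.90 × (−2.0) + 0.10 × 20 = +0.2.
- Control: 0.986 × (−0.6) + 0.014 × 20 = −0.3.

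The net difference runs from −0.9 to +0.5 points, so its sign depends on the assumptions.

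**Step 5. Scale.** With about 64 patients per arm in mITT and an assumed 40% good outcome, the standard error of a difference is √(2 × 0.40 × 0.60/64) = 8.7 points. The upper false-positive figure of 1.7 points is 0.2 standard errors.

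**The case against.** **The protocol already asks for vessel imaging before randomisation (5.42).** If that line governs, occlusion is settled before allocation and the point falls. It cannot simply be preferred, because the time-0 text in the same section and the sequence in 5.1 and 5.33 say otherwise. What stands is that this is partly an internal contradiction that must be resolved.

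**Section 5.35 concerns the decision to operate, not mITT membership.** Correct. The link is an inference from the fact that no other test of occlusion is named. The analysis plan, not shown, may say how membership is established. But the protocol itself fixes both the occlusion condition and the arm-specific imaging.

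**A blinded core laboratory reviews the images (end of 5.37).** It is not given the task of deciding membership, and blinded reading does not turn MRA and CTA into one test.

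**The effect is probably small.** On the assumed values this stands.

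Stronger conclusions are tempting and should not be drawn. A reader might infer that all of mITT is selected by different tests. Route B patients are not, and controls may also have MRA. A reader might infer that the bias favours the MRI group. The documents do not say that MRA over-calls occlusion or how misclassified patients fare, and Step 4 shows the sign can change. A reader might also infer that such a bias could never be seen. Angiography in operated patients would reveal some false positives, although no such check is planned.

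**Conclusion.** The concern holds in a limited form. For route A patients, unless everyone has the vessel imaging that 5.42 lists before randomisation, membership of the primary set can be decided after randomisation by a test that differs by arm. The non-inferiority comparison is then not fully protected by randomisation, and no all-randomised shift analysis is stated to check it against.

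Direction and size cannot be derived from the protocol. The false-positive part is 0.4 to 1.7 points under the main assumed values and 0.1 to 2.4 over the wider grid. It would shrink with the share of route B patients and of controls imaged by MRA. These figures are on a binary outcome. They have not been converted to the common odds ratio, and the protocol states no margin to set them against. The reason to act is that the protection is cheap, not that a large bias has been shown.

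**What to change.** 1. Reconcile the pre-randomisation imaging line in 5.42 with the time-0 text of that section and with 5.1 and 5.33, so that it is clear whether vessel imaging precedes randomisation in every patient.
2. In 5.34 and 5.37, require the non-inferiority conclusion to hold in all randomised patients by assigned group, whatever the vessel reading, as well as in mITT.
3. Report by arm how many randomised patients were left out of mITT because no occlusion was found.
4. One vessel definition, read by the existing blinded core laboratory, may support mITT. It does not by itself remove the difference between arms. DSA exists only for operated patients, so it should not decide membership: verification would then depend on the arm's treatment decision.

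The cost is one further analysis of 90-day mRS, which is already to be collected, and some wording. The downside is that the all-randomised set includes patients without occlusion and is diluted towards no difference, which in a non-inferiority trial makes the conclusion easier to reach. It should therefore be required alongside mITT and not replace it.
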